COMIRB Protocol

COLORADO MULTIPLE INSTITUTIONAL REVIEW BOARD
[name] [contact] [contact]

Protocol #: 16-1479
Project Title: The impact of estrogen status on the biological function of brown adipose tissue in women measured using quantitative PET/CT
Principal Investigator: [name].
Version Date: 2/7/2022

I. Hypotheses and Specific Aims: The physiological relevance of brown adipose tissue (BAT) in humans is largely unknown. We have shown that suppressing ovarian function in premenopausal women reduces resting energy expenditure (REE), and this is prevented by adding back estradiol (E₂). Our preliminary data suggest that this may be due, in part, to reduced brown adipose tissue (BAT) activity. Our overarching hypothesis is that BAT activity in humans is modulated by E₂. To determine if natural declines in endogenous E₂ contribute to changes in BAT activity, we will compare BAT activity in pre-and post-menopausal women. We will also explore whether suppression of ovarian hormones in pre-menopausal women impairs BAT activity. BAT activity will be quantified using dynamic positron emission topography/computed tomography (PET/CT) imaging combined with ¹¹C-acetate tracers. We will assess the thermogenic response of BAT by measuring cold-induced changes in REE, shivering, and skin and core temperature.

SA1: To determine if menopausal state influences constitutive BAT oxidative metabolism and activity volume under thermoneutral conditions (room temperature).

H1_a: BAT oxidative metabolism and activity volume will be greater in pre- than postmenopausal women

H1_b: REE will be associated with BAT oxidative metabolism and activity volume.

SA2: To determine if menopausal state influences stimulated BAT oxidative metabolism and activity volume in response to very mild cold exposure.

H2_a: In response to a mild cold exposure, BAT oxidative metabolism and activity volume will be greater in pre- than postmenopausal women

SA3 (exploratory): To determine whether 6 mo. GnRH_{AG} in premenopausal women attenuates basal and stimulated BAT oxidative metabolism and activity volume.

H3_a: Basal and cold-stimulated BAT oxidative metabolism and activity volume will be reduced after GnRH_{AG}.

H3_b: The decrease in REE after GnRH_{AG} will be associated with the decrease in BAT oxidative metabolism and activity volume.

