II. Background and Significance: In rodents, the loss of ovarian function disrupts energy balance resulting in excess fat gain, and that this is prevented or reversed by estradiol (E₂).^{71,75,89} In premenopausal women, we have shown that suppressing ovarian function decreases in REE (~50 kcal/d),^{22,49} independent of changes in body composition,²² which may contribute to the risk for weight gain and obesity-related diseases that occurs with menopause.^{35,45,88} We have also shown that replacing E₂ prevents this decrease in REE.⁴⁹ **However, the mechanisms by which the loss of E₂ suppresses REE in women remain unknown.**

In humans, assessing the metabolic activity of BAT *in vivo* is challenging. Most studies have assessed ¹⁸F-fluoro-2-deoxyglucose (¹⁸FDG) uptake using PET/CT.^{4,38,39} This approach provides an indication of the volume of active BAT, but is not a quantitative marker of BAT metabolic activity.⁴ In contrast, dynamic PET imaging (i.e., series of frames over contiguous time intervals) combined with metabolic tracers (e.g., ¹¹C-acetate) provides a quantitative measure of *in vivo* BAT metabolic activity. Using this approach, we have confirmed that BAT metabolic activity (clearance rate of ¹¹C in BAT after ¹¹C-acetate administration) increases in men exposed to a mild cold stimulus.^{6,58} We have also demonstrated that BAT is

metabolically active in humans under thermoneutral conditions,⁶ but have not yet quantified the contribution of this activity to REE.

Our overarching hypothesis is that BAT activity in humans is modulated by E₂. Specifically, we will determine if BAT metabolic activity contributes to resting energy expenditure (REE), and whether BAT metabolic activity under basal and stimulated conditions is modulated by estrogen status. We will assess the contribution of BAT metabolic activity to REE under both basal (thermoneutral) and stimulated (cold exposure) conditions. We will compare BAT oxidative metabolism (¹¹C clearance rate in BAT) and BAT activity volume (volume of ¹⁸FDG uptake) in pre- and postmenopausal women, and in a subset of premenopausal women after 6 mo. of ovarian hormone suppression using gonadotropin releasing hormone agonist (GnRH_{AG}) treatment.

III. Preliminary Studies/Progress Report:

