Estrogen and fat gain: Basic and preclinical studies provide evidence that the loss of E₂ or E₂ signaling causes excess fat gain^{32,37,72,89,90} which is prevented by E₂ treatment.⁵⁰ In humans, suppression of gonadal function by gonadotropin releasing hormone agonist (GnRH_{AG}) therapy causes excess fat gain^{24-26,65,90} and abdominal fat accrual.⁷⁵ In both women⁷⁵ and men,²⁶ evidence suggests that such changes are specifically related to E₂ deficiency. A system-level mechanism that contributes to excess fat gain in response to E₂ suppression is a reduction in total energy expenditure (TEE).^{13,90} We have demonstrated that, like OVX and disruption of E₂ signaling in animals, suppression of ovarian function in women causes a decrease in REE and TEE. We have used a pharmacological approach (gonadotropin releasing hormone agonist, GnRH_{AG})

to suppress ovarian function to explore the role of E₂ in modulating REE. In our first study in premenopausal women (N=14), REE was significantly lower after 6 days of sex hormone suppression (1334±36 kcal/d, mean±SE) when compared with the mid-luteal phase (1405±42 kcal/d) or the early follicular phase (1376±43 kcal/d).²² This also reduced SNS support of REE.²¹ In our recently completed study,^{49,75} 70 premenopausal women were randomized to 5 months of GnRH_{AG} with (GnRH_{AG}+E₂) or without (GnRH_{AG}+PL) E₂ add back. Our major findings were that GnRH_{AG}+PL caused a decrease in REE (-57±105 kcal/d), which was prevented by E₂ (-4±75 kcal/d). Total daily energy expenditure (TDEE) was also decreased in response to GnRH_{AG}+PL (-128±42 kcal/d), but this was not fully prevented by GnRH_{AG}+E₂ (-96±30 kcal/d) (Figure 1).

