CIT varies with E₂: We recently performed a pilot study in healthy, premenopausal women (n=5; 31 \pm 6 yr.; BMI 24.3 \pm 4.5 kg/m²) to determine the effects of ovarian hormone suppression on REE, CIT, and BAT activity. Before and after 3 mo of GnRH_{AG}, participants underwent a 2-hr cooling protocol using a surgical cooling vest filled with water (~16–18° C). Following GnRH_{AG}, REE decreased from 1382 \pm 218 kcal/d to 1341 \pm 209 kcal/d; the decrease (-41 \pm 160 kcal/d) was similar in magnitude to that observed in response to 5 mo of GnRH_{AG}+PL in the study described above (-57 \pm 105 kcal/d). CIT was also attenuated (350 \pm 228 vs. 302 \pm 139 kcal/d, Figure 4). We also performed ¹⁸FDG PET/CT measurements to demonstrate the feasibility of measuring BAT activity with this protocol. After GnRH_{AG}, no significant differences in ¹⁸FDG uptake were observed, but ¹⁸FDG uptake in BAT decreased in 3 of the 5 individuals studied (Figure 5). There are two limitations to consider in this pilot study. Firstly, the period of hormone suppression may have been too short to invoke substantial changes in BAT activity and CIT, because a single injection of GnRH_{AG} produces an initial sex hormone flare (for up to 3 wk) followed by continuous suppression with additional doses of GnRH_{AG}. **In the proposed study, we will use a longer period of ovarian suppression (6 mo) (SA3, exploratory).** Secondly, the use of ¹⁸FDG PET/CT to study BAT metabolism is influenced by the energy status of the BAT. Because FM increased following GnRH_{AG}, BAT TG content may have also increased, which will reduce ¹⁸FDG uptake independent of any changes in BAT metabolism.⁴ **In the proposed study, in addition to ¹⁸FDG, we will use PET to measure clearance of the tracer ¹¹C-acetate in BAT, which is not dependent on the energy status of the tissue and provides a direct measure of BAT thermogenesis.** We expect to see a more clear suppression of BAT thermogenesis with a more prolonged period of ovarian suppression (pre- vs. postmenopausal women, **SA1 and SA2; 6 mo**).

[figure not shown]

Fig 3. ¹¹C-acetate uptake during warm and cold-stimulated conditions. Ouellette et al., J Clin Invest, 2012

[figure not shown]

Fig 4. Cold-induced thermogenesis in pre-menopausal women before and after 3 mo. GnRHAG treatment.

[figure not shown]

Fig 5. Change in maximal standardized uptake values (SUV) of ¹⁸FDG in BAT in pre-menopausal women N=5) before and after 3 mo. GnRHAG treatment.

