- **Leuprolide acetate** – A subset of premenopausal women will receive GnRH_{AG} (leuprolide acetate) 3.75 mg/mo by intramuscular injection every 4 weeks for 24 weeks (6 doses).
 - Contraindications for use include: hypersensitivity to GnRH, GnRH agonist analogs or any of the excipients in Lupron Depot; undiagnosed vaginal bleeding; known or suspected pregnancy; lactation.
 - In women who are pregnant, use of leuprolide acetate may cause fetal abnormalities.
 - Leuprolide acetate may cause an anaphylactic reaction in volunteers with hypersensitivity to GnRH.
 - Regular menstruation should stop during leuprolide acetate therapy but spotting or breakthrough bleeding may occur. Cessation of menses does not ensure that pregnancy will not occur. Normal menstrual function is usually restored within 2-3 months after therapy is discontinued.
 - Leuprolide acetate may cause symptoms related to hypoestrogenism including hot flashes, headaches, nausea, emotional lability, decreased libido, acne, myalgia, sleep disorders, reduction in breast size, hypertension, and vaginal dryness. Bone loss may occur, although the amount lost over the 24-week intervention should be recovered slowly after discontinuation of leuprolide acetate treatment. There may be a development or worsening of depression and the occurrence of memory disorders
 - In rare cases, leuprolide acetate may cause seizures (post-marketing concern).
 - Leuprolide acetate therapy for 24 weeks may cause an increase in FM (~1.0-1.5 kg), a decrease in fat-free mass (1-1.5 kg), an increase in total, LDL, and HDL cholesterol (5-10%), and an increase in triglycerides (15-20%).
 - Local injection site reactions including induration and abscess may occur.
- **Risk of radiation exposure:** Participants will be exposed to radiation during the PET/CT and DXA scans. During the PET/CT scans, participants are exposed to radiation from the CT and from the radiopharmaceuticals. The primary risk of this level of radiation exposure is to the unborn fetus of pregnant women. All participants will perform one DXA and PET/CT study, and a subset of premenopausal women will perform these tests twice. The estimated radiation exposure during each study visit is listed in the table below

Table 2. Estimated radiation exposure (mSv)

Visit #	C-11	F-18	CT	DXA
0				0.015
1	0.91		0.96	
2	0.91	3.5	0.96	
			2.55	
8				0.015
8	0.91		0.96	
9	0.91	3.5	0.96	
			2.55	

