There is no known way to distinguish the energy expenditure associated with shivering and non-shivering thermogenesis in humans. Thus, we will employ rigorous techniques to measure shivering during cold exposure using both sEMG and ¹⁸FDG uptake into deep muscles. These data will be used to quantify shivering and used to interpret differences and changes in CIT.

Postmenopausal women will likely have higher levels of body fat, and body fat may increase in premenopausal women after GnRH_{AG}. As described above, the cooling suit delivers an identical cold stimulus during each study. Our intent is not to determine the maximal activity of BAT, but rather, determine if differences in BAT activation in response to a constant stimulus is either different between pre- and postmenopausal women (**SA2**), or changes after GnRH_{AG} (**SA3**). To account for differences or changes in body composition, REE will be expressed per kg of fat free mass.

We acknowledge that GnRH_{AG} causes a more abrupt withdrawal of ovarian function (i.e., weeks rather than years) and does not generate the same gonadotropin response of menopause (i.e., low rather than high). However, the GnRH_{AG} model is also a strength because it allows us to control the sex hormone environment in a manner that is not possible when studying the natural menopause transition.

F. Data Analysis Plan:

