Analysis strategy - Statistical analyses will be performed using SAS 9.4. Analyses will begin with descriptive plots of individual variables to evaluate distributional characteristics and for quality assurance. The effect of menopausal status on each endpoint will be estimated using a linear regression model. The endpoint will be the response variable and a variable indicating menopausal status will be the explanatory variable (equivalent to a 2-sample t-test). If a variable that is related to the response variable is not balanced between menopausal groups, that variable will be included in the regression model to eliminate the potential of the effect of menopausal status being confounded by that variable. For all multivariable analyses, regression diagnostics will be used to ensure that the group of explanatory variables are not collinear. Secondary analyses will be performed to investigate whether REE is associated with either BAT

oxidative metabolism or BAT activity volume. Exploratory analyses will investigate the changes in BAT oxidative metabolism and BAT volume of activity associated with GnRH_{AG} treatment (Aim 3) Because these aims are exploratory, results will be reported using descriptive statistics, mean change, and 95% confidence intervals (CIs) for the changes in the primary and secondary endpoints.

G. Summarize Knowledge to be Gained:

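### Dividing REE by fat-free mass assumes strict proportionality and ignores fat mass, so it can hide part of the REE fall in SA3 and distort the REE-BAT association in H1b

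*Combined protocol and SAP*

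**What the plan says.** Section IV.E (Potential Scientific Problems) notes that "Postmenopausal women will likely have higher levels of body fat" and that body fat may rise on the GnRH agonist. Its remedy is: "To account for differences or changes in body composition, REE will be expressed per kg of fat free mass". No other correction of REE for body composition is given.

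REE enters two hypotheses in section I. H1b says "REE will be associated with BAT oxidative metabolism and activity volume". H3b, which is exploratory, links the REE decrease after GnRH agonist to the decrease in BAT measures.

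On analysis, section IV.F says "Secondary analyses will be performed to investigate whether REE is associated with either BAT" oxidative metabolism or activity volume, and names neither the scale of REE nor any covariates. For Aim 3 it promises descriptive statistics, mean changes and confidence intervals, with no model for H3b. Its rule for adding unbalanced variables belongs to the model for the effect of menopausal status.

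Among the possible effects of 24 weeks of leuprolide, section IV.D lists "a decrease in fat-free mass (1-1.5 kg") and a rise of about 1.0-1.5 kg in fat mass.

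**The concern.** If REE equals an intercept plus a slope times FFM, and the intercept is positive, REE per kg rises whenever FFM falls, even with no change in metabolism at a given FFM. In SA3 that runs against the REE decrease that H3b presupposes. The FFM change the protocol mentions is large enough, relative to the REE falls it cites, for the choice of scale to affect the result.

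The ratio also does not address the problem it is offered for. The paragraph is about fat, and dividing by FFM leaves any contribution of fat to REE where it was. Section III reports that cold-induced BAT activity is inversely associated with body fatness. If fat also contributes to REE at a given FFM, omitting it confounds H1b.

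Finally, because IV.F names no scale, raw, ratio and adjusted REE all remain open once the data have been seen.

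**Working it through.** The plan states no power, effect size or precision for REE, so there is no figure to reproduce.

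**Inputs from the documents**
- REE before GnRH agonist in the five-woman pilot (section III): "REE decreased from 1382" to 1341 kcal/d, a fall of 41.
- Five-month study (section III): GnRH agonist plus placebo "caused a decrease in REE (-57±105 kcal/d"). The spread is unlabelled and is taken here as an SD.
- Possible FFM loss d over 24 weeks (section IV.D): 1-1.5 kg.
- SA3 sample size: 15.

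**Assumed, because the documents do not give them**
- Baseline FFM F: 40-50 kg.
- Intercept a of REE on FFM: 0, 300 or 600 kcal/d.

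The three REE and FFM figures come from different treatment durations (3 months, 5 months, 24 weeks), so combining them is illustrative.

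**1. Artefact in SA3.** Let REE = a + b·FFM, with b = (1382 − a)/F. If FFM falls by d and nothing else changes, the ratio goes from a/F + b to a/(F − d) + b. Expressed at baseline FFM, the false rise is a·d/(F − d).

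| a (kcal/d) | smallest: F = 50, d = 1 | largest: F = 40, d = 1.5 |
|---|---|---|
| 0 | 0 | 0 |
| 300 | 300/49 = 6.1 | 450/38.5 = 11.7 |
| 600 | 600/49 = 12.2 | 900/38.5 = 23.4 |

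**2. Central case (F = 45, d = 1.25, raw fall 57).** Raw REE falls 57/1382 = 4.1%. The ratio goes from 1382/45 = 30.71 to 1325/43.75 = 30.29, a fall of 1.4%. At the follow-up FFM of 43.75 kg that is 57 − 30.71 × 1.25 = 18.6 kcal/d. The FFM-adjusted fall is 57 − b × 1.25, and on this scale the hidden amount is a·d/F.

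| a | b | FFM-adjusted fall | shown by ratio | hidden | share hidden |
|---|---|---|---|---|---|
| 0 | 30.71 | 18.6 | 18.6 | 0 | 0% |
| 300 | 24.04 | 26.9 | 18.6 | 8.3 | 31% |
| 600 | 17.38 | 35.3 | 18.6 | 16.7 | 47% |

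**3. Pilot fall of 41 with d = 1.5.** The ratio is flat or rises. At F = 50 it goes from 27.64 to 1341/48.5 = 27.65 (+0.03%). At F = 40 it goes from 34.55 to 1341/38.5 = 34.83 (+0.8%). The FFM-adjusted fall, 41 − 1.5b, is still 0.4 kcal/d (F = 40, a = 300) to 17.5 kcal/d (F = 50, a = 600).

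**4. H1b association.** Assume FFM 45 kg (SD 5), residual REE SD 100 kcal/d, no true REE-BAT link, and a BAT-FFM correlation of −0.3. To first order, the SD of the ratio due to FFM is 5a/45², and that due to residual REE is 100/45 = 2.22.
- a = 300: 0.741/√(0.741² + 2.22²) = 0.32; times 0.3 gives a false correlation of about +0.10.
- a = 600: 1.481/√(1.481² + 2.22²) = 0.55; times 0.3 gives about +0.17.

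Simulation gave 0.10 and 0.17. The signs reverse if BAT correlates +0.3 with FFM, and the effect vanishes if that correlation or a is zero. The FFM-adjusted partial correlation stayed near 0 throughout. With a real link built in (partial correlation about 0.28), the ratio gave 0.36 or 0.18 at a = 300, and 0.39 or 0.08 at a = 600, according to the sign of the BAT-FFM correlation.

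**5. Precision of SA3.** With SD 105 and n = 15, the 95% half-width for mean REE change is 2.145 × 105/√15 = 58 kcal/d.

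**The case against.** The strongest reply is that the bias is conditional and the stakes are small. The documents give no REE-FFM intercept and no baseline FFM; at a zero intercept the ratio is exact. The FFM loss comes from a risk disclosure of what leuprolide may do. Most of the drop from the raw 57 kcal/d in the central case is proper FFM correction. The section II statement that an REE fall was "independent of changes in body composition" shows the investigators had considered the issue, although the reference cited for it is the 6-day suppression study, which does not address loss over 24 weeks. REE is absent from the outcome list in IV.A, H1b is secondary, SA3 is exploratory, and its 58 kcal/d half-width exceeds the artefact. All of this stands and limits the weight of the point. It does not supply a reason for assuming a zero intercept, or a term for fat.

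The imbalance rule in IV.F could bring FFM or fat mass into a comparison by menopausal status. It does not reach H1b or SA3.

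A reader might also infer that the ratio masks an expected REE deficit in postmenopausal women. The documents do not support this. They hypothesise no pre/post REE difference, and they expect higher body fat in postmenopausal women without saying that FFM is lower. The direction would depend on that unstated quantity. With an assumed deficit of 50 kcal/d at equal FFM (45 kg) and a = 300, the ratio shows 38, 50 or 61 kcal/d if postmenopausal FFM is 2 kg lower, equal or 2 kg higher; at a = 600 it shows 24, 50 or 73.

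**Conclusion.** The point holds in conditional form. The plan's only body-composition correction for REE rests on an unjustified proportionality assumption and leaves out fat mass. If the intercept is positive, the ratio can hide about 6-12 kcal/d (intercept 300) or 12-23 kcal/d (intercept 600) of the REE fall in SA3, given FFM of 40-50 kg and a loss of 1-1.5 kg; at intercept 0 it hides nothing. Against raw falls of 41-57 kcal/d this could change how the result reads. For H1b a false correlation of about 0.10-0.17 in either direction is possible under the assumed BAT-FFM correlation of ±0.3. The omission of fat adds a further bias, so the net direction is uncertain.

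It would be too strong to say that the ratio certainly over-corrects, or that it conceals a planned pre/post REE contrast. Nor does the design rest on the 57 kcal/d: the sample size in IV.F is built on cold-induced thermogenesis and the BAT measures. The primary endpoint, 11C-acetate clearance, is untouched. This is a worthwhile, inexpensive improvement to a secondary analysis and an exploratory aim.

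**What to change.** Replace the ratio sentence in IV.E and add to the analysis strategy in IV.F:

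- **H1b:** REE in kcal/d as the response, regressed on the BAT measure with DXA FFM and fat mass as covariates. Show results with and without menopausal status, because including it removes the between-group variation that the estrogen hypothesis predicts.
- **SA3/H3b:** change in REE in kcal/d as the response, with change in FFM as the single first covariate given 15 women. Show the unadjusted change beside it, and add fat-mass change as a sensitivity analysis.
- **REE per kg FFM:** report descriptively only.

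This estimates the intercept instead of fixing it at zero; if proportionality is about right, little is lost. No new data are needed, since Table 1 schedules DXA at screening and Visit 8a.

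The cost is one to three degrees of freedom. With 64 women, H1b keeps 64 − 4 = 60 residual degrees of freedom, or 59 with menopausal status. With 15 women, H3b keeps 15 − 3 = 12, or 11 with fat mass. In SA3 the FFM slope will be imprecise, and if nearly every woman loses FFM, the change at constant FFM is partly an extrapolation. Change in body composition may also be an effect of treatment, so adjusted and unadjusted estimates answer different questions and both should be reported.

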GnRHAG, **SA3**) in combination with the use of ^{11}C -acetate PET methodologies.

IV. Research Methods

A. Outcome Measure(s): *The primary study outcome is BAT oxidative metabolism (^{11}C -acetate clearance rate) during basal and cold-stimulated conditions. Secondary outcomes are BAT activity volume (^{18}FDG uptake) during basal and cold-stimulated conditions; CIT; ^{18}FDG update into muscle; shivering (sEMG & ^{18}FDG uptake in deep skeletal muscles); and changes in skin and core temperature during cold exposure. Serum concentrations of hormones and metabolites will be measured primarily as descriptive variables, but we will also explore the association of these measures with the primary study outcomes.*

B. Description of Population to be Enrolled: Premenopausal volunteers will be healthy, eumenorrheic women, aged 18-50 yrs. Eumenorrheic status will be verified by regular menses (no missed cycles in previous year; cycle length 25-35 d). Postmenopausal volunteers will be healthy women who have no menses for at least 12 months; postmenopausal status will be confirmed based on FSH (≥ 50 mIU/ml). The primary **exclusion** criteria are:

- Pre- and Postmenopausal women
 - BMI >40 kg/m 2 ; we have purposely used a wide range of BMI to facilitate recruitment.
 - Thyroid dysfunction, defined as an ultrasensitive thyroid stimulating hormone (TSH) <0.5 or >5.0 mU/L (pre- and postmenopausal women); volunteers with abnormal TSH values will be re-considered for participation in the study after follow-up evaluation by the PCP with initiation or adjustment of thyroid hormone replacement.
 - Uncontrolled hypertension defined as resting systolic BP >150 mmHg or diastolic BP >90 mmHg; participants who do not meet these criteria at first screening will be re-evaluated, including after follow-up evaluation by the PCP with initiation or adjustment of anti-hypertensive medications
 - Self-reported diabetes or fasting glucose >126 mg/dL
 - Use of tobacco products (last 6 months)
 - Selective serotonin reuptake inhibitors (SSRIs) or any other medication or condition that may affect brown fat activity. The decision will be based on the judgement of the study physician and primary investigator.
 - Serious illness within the last 6 months
 - Confirmed positive COVID test within the last 6 months
- Additional exclusion criteria for postmenopausal women
 - Current use of hormonal replacement therapy or use <10 yrs ago.
 - Women who have undergone surgical menopause.

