Sample size justification and power analyses – Sample size calculations and power analyses were performed using SAS 9.4 (SAS Institute, Inc., Cary, NC). For our estimate of effect size, we refer to our previous study that measured CIT in the follicular and luteal phases (Figure 5).⁸ In that study, CIT was higher during the luteal phase ($2530 \pm 524 \text{ kcal} \cdot \text{d}^{-1}$ vs. $2225 \pm 440 \text{ kcal} \cdot \text{d}^{-1}$). Unfortunately, we did not measure BAT activity. Because there were no differences in shivering in this study, we will assume differences in CIT were due to differences in NST; we also assume that this reflects differences in BAT activity. Using a pooled SD of 484 kcal/d, 32 evaluable participants per group (64 total) will provide 80% power to detect a difference of 305 kcal/d in CIT between pre- and postmenopausal women using a 2-sided t-test and a type I error rate at 0.05. Assuming a dropout rate of 15%, 38 participants per group will need to be enrolled to yield the desired sample size of 64 participants. The primary endpoint is BAT oxidative metabolism (¹¹C clearance rate, expressed per mL of BAT per s⁻¹). In our previous study of 12 men, BAT oxidative metabolism increased during cold exposure from 0.35 ± 0.13 to 0.74 ± 0.19 (mean \pm SEM).⁶ Using a pooled SD of 0.45, we estimate that we will have 80.0% power to detect a difference between groups of 0.32 during thermoneutral conditions. Using a pooled SD of 0.66, we will have 84.7% power to detect a difference between groups of 0.50 during cold exposure. In another study, BAT oxidative metabolism at room temperature was 0.35 in lean men vs. 0.05 in overweight men with T2D.¹⁰ We have also reported that BAT oxidative metabolism increased in lean men from 0.73 to 1.59 following a 4-week cold acclimation.⁷ Thus, we consider this to be a meaningful effect size to examine differences in BAT oxidative metabolism between groups during thermoneutral conditions and during cold exposure. A secondary endpoint is BAT activity volume. In our previous study, BAT activity volume was $57 \pm 16 \text{ ml}$ (mean \pm SE).⁶ Using a pooled SD of 55 ml, the study will have 80.0% power to detect a difference of 39 mL between groups. In another study, we reported that BAT activity volume was 48 vs. 4 ml in young healthy men compared to older men with T2DM.⁵ Thus, we consider this to be a meaningful effect size.

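### The 80% power stated for cold-induced thermogenesis does not follow from its own inputs; a two-sided test at 32 per group gives 69.9%

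*Combined protocol and SAP*

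**What the plan says.** Section IV.F takes its effect size from an earlier study of CIT in two menstrual-cycle phases (2530 ± 524 and 2225 ± 440 kcal/d). With a pooled SD of 484 kcal/d it concludes that "32 evaluable participants per group (64 total) will provide 80% power to detect a difference of 305 kcal/d in CIT". The contrast meant is the one by menopausal status, and the test behind the figure is specified in the same sentence: "using a 2-sided t-test and a type I error rate at 0.05". The enrolment target follows at once: "Assuming a dropout rate of 15%, 38 participants per group will need to be enrolled".

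The same paragraph then gives power for the primary endpoint, BAT oxidative metabolism. With SD 0.45, "we will have 80.0% power to detect a difference between groups of 0.32 during thermoneutral conditions"; with SD 0.66, "we will have 84.7% power to detect a difference between groups of 0.50 during cold exposure". It also states 80.0% power for a 39 mL difference in BAT activity volume, with SD 55 mL.

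Under Analysis strategy, the group comparison is a linear regression on menopausal status, described as "equivalent to a 2-sample t-test". Covariates enter conditionally: "If a variable that is related to the response variable is not balanced between menopausal groups", it is added to the model. Section IV.A lists CIT among the secondary outcomes, after BAT activity volume ("during basal and cold-stimulated conditions; CIT").

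**The concern.** Every input to the CIT calculation is stated, so it can be checked directly, and it does not come out. A standardised difference of about 0.63 with 32 per group is too small for 80% power in a two-sided test at 0.05.

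Two things are at stake. First, this calculation introduces the sample size: 32 evaluable per group appears in the sentence and 38 enrolled in the next, so the rationale presented for N does not support N. Second, a null CIT result would be read against a sensitivity the design lacks. A reader told 80% would expect to miss a true 305 kcal/d difference one time in five; on the stated inputs it is closer to three in ten.

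**Working it through.** **Inputs, all from section IV.F**

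- Difference: 2530 − 2225 = 305 kcal/d.
- Pooled SD: √((524² + 440²)/2) = 483.8, stated as 484.
- 32 evaluable per group, two independent groups.
- Two-sided t-test, type I error 0.05.

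The difference and SD reproduce. Only the power does not.

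**Power for the stated test**

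- d = 305/484 = 0.630.
- Noncentrality = d × √(n/2) = 0.630 × √16 = 2.52, with 2 × 32 − 2 = 62 degrees of freedom.
- Two-sided power from the noncentral t: **69.9%** (stated: 80%).
- The normal approximation gives 71.2%. Varying the inputs within rounding gives 69.7% to 70.1%.

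**Can the 80% be recovered another way?**

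| Variant | Power |
|---|---|
| Two-sided, all 38 enrolled per group | 77.4% |
| Two-sided, SD 440 (the smaller of the two) | 77.9% |
| Two-sided, SD 524 (the larger) | 63.0% |
| One-sided 0.05, 32 per group | 80.2% |
| One-sided 0.05, 31 per group | 79.0% |

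Of these, only the one-sided test at 32 per group gives 80%, and 32 is the smallest group size that does so. This suggests how the figure arose, but the document does not say so. A paired calculation would need an assumed within-person correlation of about 0.25, which is not given and does not fit two separate groups of women.

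**The same method applied to the other figures (32 per group)**

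| Endpoint | Difference / SD | Stated | Two-sided | One-sided |
|---|---|---|---|---|
| Oxidative metabolism, thermoneutral | 0.32 / 0.45 | 80.0% | 79.96% | 87.9% |
| Oxidative metabolism, cold | 0.50 / 0.66 | 84.7% | 84.69% | 91.2% |
| BAT activity volume | 39 / 55 | 80.0% | 79.7% | 87.7% |

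All three match a two-sided calculation and none matches a one-sided one. CIT is the exception.

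**What the stated inputs support**

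- Detectable standardised difference at 80% power, 32 per group: 0.7115. In kcal/d, 0.7115 × 484 = 344.4, so about 344.
- Group size for 80% power at 305 kcal/d: 40 gives 79.5% and 41 gives 80.5%, so 41. Enrolled at 15% dropout: 41/0.85 = 48.2, so 49.
- Planned enrolment: 32/0.85 = 37.6, so 38, as stated.

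**Could covariate adjustment close the gap?**

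For 80% power at 305 kcal/d the residual SD must fall to 305/0.7115 = 428.7. The covariates would then have to explain 1 − (428.7/484)² = 21.6% of the variance, with no loss from correlation with group. But they are admitted because they differ between the groups, so some loss is to be expected and the net effect on power cannot be known in advance.

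**The case against.** The arithmetic has no good defence; the case on the other side concerns weight and scope.

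- **The consequence is limited.** CIT is one of several secondary outcomes, and the primary-endpoint powers reproduce at 32 per group. This stands, and it is why N need not change.
- **CIT is not the only support for N.** The paragraph gives several power statements at one sample size, and 32 per group also yields the stated 80.0% for the thermoneutral primary endpoint. That is true. Even so, the text takes its effect size from CIT and states 32 and then 38 in and immediately after the CIT calculation, so a reader will take that as the derivation.
- **The analysed scale may differ.** Potential Scientific Problems (IV.E) says REE will be expressed per kg of fat-free mass. If that carries over to CIT, an absolute SD of 484 kcal/d does not apply. This does not rescue the 80%. It does mean that 69.9% is the power for the stated inputs, not necessarily the power of the eventual CIT analysis.
- **Re-basing N goes beyond a correction.** The smallest repair is to change 80% to about 70%, or 305 to about 344. That would be accurate, but it would leave the sample size introduced by a 70% power statement. The primary-endpoint figures are already in the paragraph.

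**Conclusion.** The concern holds. Section IV.F overstates two-sided power for CIT by about ten percentage points: 69.9% against 80%. This rests only on the inputs printed there (305, 484, 32 per group, two-sided 0.05) and on the planned unadjusted two-group comparison. Nothing elsewhere in the document repairs it.

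The finding is confined to one secondary outcome and to the stated rationale for the sample size. The primary-endpoint figures are reproduced under their stated assumptions; whether those assumptions, drawn from a study of 12 men, are realistic for these women was not examined. The statement should be corrected, but the design need not change.

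**What to change.** Keep 32 evaluable and 38 enrolled per group, and reorder the paragraph so that N rests on the primary endpoint under its stated assumptions: 80.0% power for 0.32 (SD 0.45) at thermoneutrality and 84.7% for 0.50 (SD 0.66) in the cold. Place the 15% dropout sentence after those figures. Replace the CIT sentence with, for example: *For CIT, a secondary outcome, 32 evaluable participants per group give about 70% power for 305 kcal/d, or 80% power for about 344 kcal/d (SD 484, two-sided t-test, alpha 0.05).*

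The cost is a wording change in one paragraph and a less favourable stated power for CIT. No participants are added and the analysis is unchanged.

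A separate, optional check before the CIT sentence is reissued: Visit #2 defines CIT as cold-stimulated minus baseline REE, so the sponsor should confirm in its cited study whether 2530 and 2225 kcal/d are increments or total expenditure. The document points both ways.

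- The pilot in section III reports CIT of 350 and 302 kcal/d, but in five women with a cooling vest, so it is not directly comparable.
- Applying the roughly 75% rise expected at Visit #2 to the pilot's baseline REE gives a total of 1382 × 1.75 ≈ 2420 kcal/d, which lies between the two figures.
- The earlier study quoted at Visit #2, in men, implies an increment of 4170 − 2300 = 1870 kcal/d, much nearer to them.

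If they are totals, both the 305 difference and the SD should be replaced with values for the increment and CIT power recalculated; the replacement sentence above would then need new numbers. The arithmetic error stands whatever the answer.
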